### 9.6.3 Summaries of Baseline Characteristics, Demographics, and Other Analyses

#### Demographic and Baseline Characteristics

The number and percentage of participants screened, randomized, the primary reasons for screening failure, and the primary reason for discontinuation will be displayed.

Demographic variables (including age, gender, race, weight, and height), baseline characteristics, primary and co-morbid conditions, and prior and concomitant therapies will be summarized by treatment group either by descriptive statistics or categorical tables. The comparability of the treatment groups for each relevant characteristic will be assessed by the summary tables. No statistical hypothesis tests will be performed on these characteristics.

## 9.7.2 Interim Safety Analyses

Interim safety analyses will be performed periodically (determined either by calendar date or enrollment milestones, to be specified separately in the DMC charter). For these interim analyses, a general review of safety results will be performed based on review of AEs, laboratory safety parameters, and other safety endpoints.

[figure not shown]
## 9.8 Multiplicity

### Primary and Key Secondary Endpoints

Due to the interim analysis for futility, an  $\alpha$ -spending of 0.0001 will be applied to the 2-sided Type I error rate of 0.05 for the primary and secondary hypotheses based on the Haybittle Peto method [Haybittle, J. L. 1971] [Peto, R., et al 1976]. Multiplicity adjustment will be made for testing 2 doses on the primary and the key secondary endpoints for the analysis, ie, for testing a family of the following hypotheses:

- H11: MK-7264 45 mg BID is superior to placebo in reducing 24hour coughs per hour at Week 24
- H12: MK-7264 15 mg BID is superior to placebo in reducing 24-hour coughs per hour at Week 24
- H21: MK-7264 45 mg BID is superior to placebo in reducing awake coughs per hour at Week 24
- H22: MK-7264 15 mg BID is superior to placebo in reducing awake coughs per hour at Week 24
- H31: MK-7264 45 mg BID is superior to placebo on the proportion of participants with a  $\geq 1.3$ -point increase from baseline in LCQ total score at Week 24
- H32: MK-7264 15 mg BID is superior to placebo on the proportion of participants with a  $\geq 1.3$ -point increase from baseline in LCQ total score at Week 24
- H41: MK-7264 45 mg BID is superior to placebo with respect to the proportion of participants with a  $\geq 30\%$  reduction from baseline in 24-hour coughs per hour at Week 24
- H42: MK-7264 15 mg BID is superior to placebo with respect to the proportion of participants with a  $\geq 30\%$  reduction from baseline in 24-hour coughs per hour at Week 24

To strongly control the Type I error rate for this family, a step down testing procedure will be applied in the order specified above. Each hypothesis will be formally tested only if the preceding one is significant at  $\alpha=0.0499$  level.

[figure not shown]
[Redacted], [Table 6](#) provides power for the primary and key secondary efficacy endpoints with a total of 1290 participants (430 participants per treatment group). All calculations are based on 2-sided  $\alpha=0.0499$  significance level. The dropout rate is expected to be 20% at Week 24.

Table 6 Power for the Primary and Key Secondary Efficacy Endpoints

Endpoints (At Week 24)	Power in MK-7264 45 mg BID Group	Power in MK-7264 15 mg BID Group
24-hour coughs per hour	>99%	98%
Awake coughs per hour	98%	97%
Proportion of participants with $\geq 1.3$ -point increase from baseline in LCQ total score	81%	56%
Proportion of participants with $\geq 30\%$ reduction from baseline in 24-hour coughs per hour	55%	50%

BID = twice daily; LCQ = Leicester Cough Questionnaire

Note: details of the concomitant medications will be provided in a separate sSAP.

A similar longitudinal ANCOVA model as the primary efficacy endpoint will be performed.

For each subgroup, summary statistics including mean, SD, and 95% CIs will be provided for each treatment group.

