The impact of chronic cough on health-related quality of life (HRQoL) as assessed by the LCQ is included as the second secondary endpoint. The goal is to demonstrate that a greater proportion of participants treated with MK-7264 relative to placebo achieve a clinically meaningful improvement from baseline in HRQoL defined as a  $\geq 1.3$ -point increase in the LCQ total score at Week 24. The LCQ is a 19-item cough-specific HRQoL questionnaire which contains 3 domains (physical, psychological and social), calculated as a mean score for each domain ranging from 1 to 7 and total score ranging from 3 to 21. Each item on the LCQ assesses symptoms or the impact of symptoms on HRQoL over the past 2 weeks using a 7-point Likert scale ranging from 1 to 7. Higher scores indicate better HRQoL. Data obtained from the LCQ will provide information on the impact of chronic cough on patients' daily lives, beyond objective cough counts and severity, which is valuable information for assessing the full benefit of effective cough control.

[figure not shown]

Two additional patient reported outcome (PRO) measures specific to cough, the CSD and Cough Severity VAS are included as secondary endpoints to assess cough frequency, intensity, disruption due to cough and cough severity.

The CSD is a 7-item, disease-specific PRO measure with a recall period of “today”. The measure evaluates frequency of cough (3 items), intensity of cough (2 items) and disruption (2 items); each item is rated on an 11-point scale ranging from 0 to 10 with higher scores indicating greater severity. A CSD total score and 3 domain scores (frequency, intensity, disruption) can be calculated.

The Cough Severity VAS is a single-item question asking the participant to rate the severity of their cough “today” using a 100 mm VAS anchored with “No Cough” at 0 and “Extremely Severe Cough” at 100. Similar to the well-established use of VAS scores in chronic pain, the Cough Severity VAS measure provides a quick, valid and easily-interpreted subjective assessment useful for clinicians to monitor improvement of their chronic cough patients following treatment.

consistent with the provisional benchmarks outlined by the Initiative on Methods, Measurement, and Pain Assessment in Clinical Trials which recommends that an improvement of approximately 30% on a 0 to 10 numeric rating scale can be considered clinically meaningful [Dworkin, R. H., et al 2009].

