#### **4.3 Justification for Dose**

##### **4.3.1 Doses for This Study**

The dose for this study will be either MK-7264 15 mg BID or MK-7264 45 mg BID as determined by the individual allocation per the assigned treatment group (see Section 6). The known mechanism of action of MK-7264 and related clinical study results support that the efficacy of MK-7264 in decreasing cough, and the prevalence of the most common AE, dysgeusia, are both dose related. In order to allow patients and prescribers appropriate flexibility based upon individual clinical needs, the MK-7264 development program has targeted 2 different doses to study in the Phase 3 program.

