### **Responders in 24-hour Coughs per Hour**

The responder variable in 24-hour coughs per hour is defined based on the magnitude of the percent change from baseline in the original scale at each post-Baseline visit:

Participant is considered a responder if the percent change from baseline in 24-hour coughs per hour is  $\leq -30\%$ ; participant is a non-responder otherwise.

The percent change from baseline in 24-hour coughs per hour is defined as follows:

Percent change in 24-hour coughs per hour  
= (Change from baseline in 24-hour coughs per hour/Baseline 24-hour coughs per hour)\*100%

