### Secondary Efficacy Analysis

The continuous secondary efficacy endpoints will be analyzed using a similar longitudinal ANCOVA model as used for the primary efficacy analysis.

As the change in awake coughs per hour may have a skewed and wide distribution, the data will be log-transformed (natural log) prior to analysis. The variable of change from baseline in log-transformed awake coughs per hour will be used in the analysis.

Responder endpoints will be analyzed by the logistic regression model. The model will include terms for treatment group, visit, the interaction of treatment group by visit, gender, region, baseline, and the interaction of baseline by visit for the underlying continuous response. Log odds ratio will be back transformed into odds ratio for final reporting.

Table 4 summarizes the analysis strategy of the primary and key secondary efficacy endpoints.

Table 4 Analysis Strategy for Primary and Key Secondary Efficacy Endpoints

Endpoint/Variable (At Week 24)	Statistical Method	Missing Data Approach
Primary		
24-hour coughs per hour	Longitudinal ANCOVA	Model-based a
Secondary		
Awake coughs per hour	Longitudinal ANCOVA	Model-based a
Proportion of participants with a $\geq 1.3$ point increase from baseline in LCQ total score	Logistic Regression	Model-based a
Proportion of participants with a $\geq 30\%$ reduction from baseline in 24-hour coughs per hour	Logistic Regression	Model-based a
Proportion of participants with a $\geq 1.3$ point reduction from baseline in mean weekly CSD total score	Logistic Regression	Model-based a
Proportion of participants with a $\geq 2.7$ point reduction from baseline in mean weekly CSD total score	Logistic Regression	Model-based a
Proportion of participants with a $\geq 30$ mm reduction from baseline in Cough Severity VAS score	Logistic Regression	Model-based a
a Includes data collected after intervention discontinuation. ANCOVA = analysis of covariance; CSD = Cough Severity Diary; LCQ = Leicester Cough Questionnaire; VAS = Visual Analogue Scales.		

The strategy to address multiplicity issues with regard to multiple treatment comparisons, multiple efficacy endpoints, multiple timepoints, and interim analyses is described in Sections 9.7 and 9.8.

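### Should the 45 mg cough-responder test (H41) stand ahead of the 15 mg LCQ test (H32) in the fixed testing order?

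*Combined protocol and SAP*

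**What the plan says.** Section 9.8 lists H11, H12, H21, H22, H31, H32, H41, H42. The first digit is the endpoint (24-hour coughs, awake coughs, LCQ responder, cough responder) and the second is the dose (1 for 45 mg, 2 for 15 mg). The rule is: "To strongly control the Type I error rate for this family, a step down testing procedure will be applied in the order specified above". A later test needs the one before it to succeed: "Each hypothesis will be formally tested only if the preceding one is significant at" 0.0499.

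In Section 9.9, Table 6 "provides power for the primary and key secondary efficacy endpoints with a total of 1290 participants", 430 per arm. For 45 mg and 15 mg it gives >99% and 98% (24-hour coughs), 98% and 97% (awake coughs), 81% and 56% (LCQ), and 55% and 50% for the responder row defined by a 30% "reduction from baseline in 24-hour coughs per hour". The words that introduce the table are redacted. The visible text does not say whether the entries are cumulative along the sequence or stand-alone.

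Two other places bear on the order. Section 4.2.1.1 says of LCQ that it "is included as the second secondary endpoint". Section 4.3.1 says that "the MK-7264 development program has targeted 2 different doses to study in the Phase 3 program".

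**The concern.** H41 tests the higher dose on an endpoint cut from the primary variable, yet it can be reached only if the lower dose first succeeds on a questionnaire endpoint. In test order Table 6 reads >99, 98, 98, 97, 81, 56, 55, 50. It never rises, as cumulative power must not. Read that way, H32 passes 56/81 = 69% of the time once reached, while H41 passes 55/56 = 98%. Among the last four tests, the one with the best conditional chance waits behind the one with the worst. Over all eight that is not so, since H11, H12, H21 and H22 each have a higher conditional rate than H41.

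At stake would be about 24 points of power for a key secondary hypothesis, apparently recoverable by exchanging two neighbours with no extra participants.

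**Working it through.** **Inputs.** Order, gate rule and Table 6 entries are from Sections 9.8 and 9.9. The entry >99% is taken as 99.5% (assumption). The level reproduces: 0.05 − 0.0001 = 0.0499, two-sided critical value 1.961. Table 6 itself cannot be rebuilt, because the effects and rates behind it are redacted. That is not counted against the plan.

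**Both readings.** The conditional column is each entry divided by the one before it. The chain column is the running product of the entries, treated as independent stand-alone powers.

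| Test | Table 6 | Conditional pass rate (cumulative reading) | Chain product (stand-alone, independent) |
|---|---|---|---|
| H11 | >99% | 99.5% | 99.5% |
| H12 | 98% | 98.5% | 97.5% |
| H21 | 98% | 100% | 95.6% |
| H22 | 97% | 99.0% | 92.7% |
| H31 | 81% | 83.5% | 75.1% |
| H32 | 56% | 69.1% | 42.0% |
| H41 | 55% | 98.2% | 23.1% |
| H42 | 50% | 90.9% | 11.6% |

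**Which reading?** The falling order is weaker evidence than it looks. Four of the seven steps go from 45 mg to 15 mg on one endpoint and would fall on either reading, since Section 4.3.1 calls efficacy dose related. The drop from 97 to 81 is also possible on either. That leaves a tie (98, 98) and one point (56, 55). Information retained is better evidence. For 15 mg, 98% on the continuous endpoint needs a noncentrality of 1.961 + 2.054 = 4.01.
- Stand-alone, the responder test at 50% has 1.96, and (1.96/4.01)² = 24% of the information.
- Cumulative, 50/55 = 90.9% gives 1.961 + 1.335 = 3.30, and (3.30/4.01)² = 67%.

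The second is the more ordinary loss for a dichotomy of the same variable ("Participant is considered a responder if the percent change from baseline in 24-hour coughs per hour is" −30% or lower) whose model keeps "baseline, and the interaction of baseline by visit for the underlying continuous response". So cumulative is likely, but inferred.

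**Exchange, cumulative reading, planned effects.**
- H41 = 0.81 × 55/56 = 79.5%, against 55%. Simulation across assumed correlations gave 79.3–79.6%. Rounding of the entries gives about 77–82%. Table 6 alone bounds it between 55% and 0.81 − (0.56 − 0.55) = 80%.
- H32 = 0.56 × 55/56 = 55%, a loss of 1 point (0–2 with rounding).
- H42 stays at 50%, since all the tests before it must still pass.

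**Smaller responder effect only.** The H41 noncentrality is 1.961 + 2.100 = 4.061.
- 20% smaller: Φ(0.8 × 4.061 − 1.961) = 0.901. H32 = 0.56 × 0.901 = 50.5%, a loss of 5.5 points. H41 = 0.81 × 0.901 = 73.0%, against 50.5% in the present order.
- 30% smaller: Φ(0.7 × 4.061 − 1.961) = 0.811. H32 = 45.4%, a loss of 10.6. H41 = 65.7%, against 45.4%.

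These losses hang on the ratio 55/56 of two rounded numbers. Within rounding they run from about 0.4 to 8 points and from 1.6 to 14.

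**Break-even.** With p the conditional pass rate of H41, H32 loses 0.56(1 − p) and H41 gains (0.81 − 0.56)p. They are equal at p = 0.56/0.81 = 0.691, a noncentrality of 1.961 + 0.499 = 2.460. Since 2.460/4.061 = 0.61, that is about 39% below plan (about 34% to more than 50% with rounding).

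**Exchange, stand-alone reading, independent tests.** H41 = 0.751 × 0.55 = 41.3%, against 23.1%. H32 = 0.413 × 0.56 = 23.1%, against 42.0%, a loss of about 19 points.

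**The case for a change.** The best case for exchanging the two runs as follows. Any order fixed in advance controls Type I error, so nothing is lost there. On the likelier reading H41 gains about 24 points for 1 point of H32. If only the 15 mg LCQ effect is 20% smaller, H41 gains about 39 points and H32 loses 0.7. H32 loses more than H41 gains only when the responder effect alone falls far short of plan. If Table 6 is stand-alone instead, it overstates what the sequence delivers: simulation under assumed correlations gives H41 about 23–33% rather than 55%, and H42 about 12–25% rather than 50%.

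The arithmetic stands, given the reading. The inference to a change does not, for three reasons.

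- A sum of power points treats the two claims as equal in worth. H41 restates, as a responder rate, an effect already tested for 45 mg at H11. H32 is separate patient-reported evidence for the lower dose. Power does not settle which should come first. The sponsor ranked LCQ above the responder endpoint and takes both doses through each endpoint before moving on.
- The small cost to H32 depends on the inferred reading. On the other reading the same exchange takes about 19 points from H32 under independence.
- Restating the two responder rows would be due only if Table 6 is stand-alone. The visible text does not show that, and the comparison of retained information (24% against 67%) argues against it.

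Nor is the exchange merely one line. Section 9 requires a protocol amendment for a change of this kind. It would also have to be settled before the interim efficacy analysis at about 40% of participants (Section 4.1), after which Section 9.2 allows the sponsor's oversight committee to see treatment-level results.

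**Conclusion.** No change to the plan. H32 does gate H41, but that is the ordinary consequence of a valid fixed sequence that follows the stated endpoint ranking and the two-dose aim. If Table 6 is cumulative, the exchange would move H41 from 55% to about 79.5% and H32 from 56% to 55% at the planned effects, with a larger and imprecise cost to H32 if the responder effect disappoints. If it is stand-alone with independent tests, H32 would drop from 42% to 23%. The gain is real on the likelier reading, but it is bought by making a 15 mg patient-reported claim conditional on a 45 mg cut of the primary variable. Statisticians could reasonably choose either order, and the sponsor's choice is a fair trade-off. The figures rest on the inferred reading of Table 6, on 99.5% for its first entry, on assumed correlations, and on H41 passing about as often when H32 fails as when it succeeds.

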### **9.11 Compliance (Medication Adherence)**

For each participant, percent compliance will be calculated using the following formula:

$$\text{Percent Compliance} = \frac{\text{Number of Days on Therapy}}{\text{Number of Days Should Be on Therapy}} \times 100\%$$

A day within the study will be considered an “On-therapy” day if the participant takes all required study intervention as instructed in Section 8. When a participant takes less than or more than the required study intervention on a day, that day is not considered an On-therapy day.

For participants who are followed for the entire study period, the “Number of Days Should be on Therapy” is the total number of days from the first scheduled intervention day to the last scheduled intervention day. For participants who discontinue from the study permanently, the “Number of Days Should Be on Therapy” is the total number of days from the first scheduled intervention day to the last dose day.

Summary statistics will be provided on percent compliance by treatment group for the APaT population.

### **9.12 Extent of Exposure**

The duration of intervention for each participant will be evaluated by calculating the number of days on therapy. Exposure to study intervention will be summarized using descriptive statistics (mean, SD, median, minimum, and maximum) for the APaT population.

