## 4 STUDY DESIGN

### 4.1 Overall Design

Approximately 1290 participants who meet entry criteria will enter the study. The duration of intervention for each participant is as follows:

- Screening Period: a minimum of 7 days and up to approximately 14 days (see Section 8.10.1)
- Baseline: 1 day (including 24 hours of objective measurement of cough) (see Section 8.10.2)
- Main study period (24-week treatment period after Baseline): 168 days (see Section 8.10.3)

- Extension study period (28-week treatment period after the Main study period): 197 days (see Section 8.10.4)
- Follow-up period: 14 days (see Section 8.10.6)

During the Main study period, participants may be required to be seen by study site personnel for 2 consecutive days (eg, Visit 2 to Visit 3, the day before Visit 4 and Visit 4, the day before Visit 5 and Visit 5, the day before Visit 6 and Visit 6, the day before Visit 7 and Visit 7, the day before Visit 8 and Visit 8 and the day before Visit 9 and Visit 9) so that the cough monitor can be attached and removed (see Section 1.3). Study site staff or mobile research nurse services may be utilized (if locally available and approved for use), so participants have the opportunity to travel to the study site on 1 day instead of traveling to the study site for 2 consecutive days.

Individual participation is expected to be approximately 56 weeks from Screening through the Follow-up period.

Specific procedures to be performed during the study, as well as their prescribed times and associated visit windows, are outlined in the SoA in Section 1.3. Details of each procedure are provided in Section 8.

This study will use an adaptive design based on pre-specified criteria, using an independent, external Data Monitoring Committee (DMC) to monitor safety and efficacy. There will be 1 planned interim efficacy analysis when approximately 40% of the total randomized participants have completed, or discontinued prior to completion of the Main study period. The study may be stopped for futility according to the results of the interim analysis.

Results of the interim analysis will be reviewed by the external DMC, which will make recommendations to the Executive Oversight Committee (EOC) of the Sponsor to continue, modify or stop the study according to the plan described in Section 9.

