### **8.1.9 Study Intervention Administration**

The distribution of study intervention will be witnessed by the investigator and/or study staff at the study site visits. Since MK-7264 45 mg and 15 mg will differ in appearance and have corresponding matching placebos, participants will receive 2 study intervention bottles (ie, either MK-7264 45 mg and placebo matched to MK-7264 15 mg OR MK-7264 15 mg and placebo matched to MK-7264 45 mg OR placebos matched to MK-7264 45 mg and 15 mg). Participants should be instructed to take 1 tablet from each bottle BID.

Study intervention should begin on the day of intervention allocation/randomization and will be administered at the study site at Visit 3. This first dose of study intervention at Visit 3 should be administered after the cough monitor is removed, after the pre-dose PK sample collection, and before approximately 11 AM. As dosing is BID, the next dose should be taken orally in the evening, approximately 12 hours later. Subsequent dosing will be performed by the participant (ie, unsupervised at his/her home) BID, approximately 12 hours apart at approximately the same time each day. However, on the day of a study site visit, the morning dose should *not* be taken at home and instead will be given as a witnessed dose at the study site, after the cough monitor is removed, after the pre-dose PK sample collection, and before approximately 11 AM (see Section 8.2.1 for further details).

On the day before Visits 4, 5, 6, 7, 8, and 9, the morning dose should *not* be taken at home and instead will be given as a witnessed dose at the study site. If the attachment of the cough monitor is to be managed by study site staff or a mobile nurse (where locally available and approved per regulations), the morning dose will be a witnessed dose with the study site staff or mobile nurse, at the participant's home. The cough monitor should be attached prior to dosing and TURNED ON immediately AFTER dosing, before approximately 11 AM (see Section 8.2.1 for further details).

Following the last Main study period visit (ie, Visit 9), participants will continue their assigned intervention in the Extension study period. The last dose of study intervention will be on the evening prior to Visit 13. Study intervention supplies will be collected at Visit 13 or Discontinuation.

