### **8.5 Treatment of Overdose**

In this study, an overdose is any dose higher than the amount of study intervention taken outside the intervention assignment (Section 4.3.2). Study intervention should be taken once in the morning and once in the evening. If more than the protocol-specified intervention is taken within a 1-day period (ie, >2 tablets/day from either bottle) this is regarded as an overdose.

No specific information is available on the treatment of overdose. Oral doses of up to 1800 mg BID for 14 days were explored in earlier clinical studies without any untoward clinical effects (see MK-7264 IB). Overdose should be treated according to the participant's clinical signs and symptoms.

Decisions regarding dose interruptions or modifications will be made by the investigator in consultation with the Sponsor Clinical Director based on the clinical evaluation of the participant.

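### Section 9.12 measures duration of intervention with the compliance day count of Section 9.11, so the exposure summary would understate time on study drug

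*Combined protocol and SAP*

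**What the plan says.** Section 9.12 (Extent of Exposure): "The duration of intervention for each participant will be evaluated by calculating the number of days on therapy". The result is summarized for the APaT population by mean, SD, median and range. The section names no first-to-last-dose duration and no cumulative dose.

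Section 9.11 (Compliance) uses the same day count as the numerator of percent compliance. A day counts "if the participant takes all required study intervention as instructed in Section 8", and the rule excludes departures in both directions: "When a participant takes less than or more than the required study intervention on a day, that day is not considered an On-therapy day".

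Section 8.1.9 sets the required intake. Every participant has two bottles, and "Participants should be instructed to take 1 tablet from each bottle BID". That is four tablets a day. In an active arm two of the four are active and two are dummy placebo. On the end of dosing it says: "The last dose of study intervention will be on the evening prior to Visit 13".

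Section 4.1 gives the planned lengths: "Main study period (24-week treatment period after Baseline): 168 days" and "Extension study period (28-week treatment period after the Main study period): 197 days". Section 4.3.2 puts planned exposure to MK-7264 at about 365 days.

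**The concern.** Duration of exposure and compliance answer different questions. Duration says how long a participant was on the assigned treatment. Compliance says how faithfully it was taken during that time. If 9.12 takes its day count from 9.11, the plan reports the second quantity under the name of the first, and no section summarizes the first.

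The 9.11 rule suits compliance but not exposure:

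- A day on which one of the two daily doses was taken scores zero.
- A day on which an active-arm participant took both active tablets but missed a dummy tablet scores zero, although the full active dose was taken.
- A day with too many tablets also scores zero.

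The count can never exceed the number of days on which something was taken, so the error runs only towards understatement.

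Safety and tolerability is a primary objective (Section 3), and Section 4.3.3 justifies the extension partly by longer-term safety. The 9.12 summary is where a reader would look to see whether about a year of exposure was reached.

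**Working it through.** **Inputs**

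- Main study period 168 days, Extension study period 197 days (Section 4.1).
- First dose at Visit 3, Day 1. Last dose on the evening before Visit 13, which is scheduled for Day 365 (Sections 1.3 and 8.1.9).
- A day counts only with exactly the required intake (Section 9.11).
- Compliance: no expected value in the documents. The levels below are assumptions. Section 6.4 uses 80% between visits as the level below which the investigator consults the Sponsor, but does not say that this is a count of fully dosed days.

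**Step 1. The plan's own figure.** 168 + 197 = 365 days, which agrees with the approximate 365 days in Section 4.3.2. Dosing from Day 1 to Day 364 gives 364 days, and 52 × 7 = 364. The two agree within the plan's rounding. I use 364, because no dose is taken on Day 365.

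**Step 2. First-to-last-dose duration for a completer.** 364 − 1 + 1 = 364 days, however many days were imperfectly dosed.

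**Step 3. The 9.11 count for the same completer.** Counted days = 364 × c, where c is the share of days dosed exactly as required.

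| Assumed c | Counted days | Shortfall from 364 |
|---|---|---|
| 99% | 360.4 | 3.6 |
| 95% | 345.8 | 18.2 |
| 90% | 327.6 | 36.4 |
| 80% | 291.2 | 72.8 |

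**Step 4. How modest lapses become lost days.** Suppose one of the two daily doses is missed once a week.

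- Days lost: 364 / 7 = 52. Counted days: 364 − 52 = 312.
- Doses taken: (2 × 364 − 52) / (2 × 364) = 676 / 728 = 92.9%.
- Every one of the 364 days still had a dose.

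If instead each dosing time is missed at random with probability m, counted days are 364 × (1 − m)². This gives 356.8 at m = 1% and 294.8 at m = 10%. Days with at least one dose are 364 × (1 − m²), which is 364.0 and 360.4. The gap between the two is time on treatment that the 9.11 rule does not count.

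**The case against.** **Section 9.12 does not cite 9.11.** It uses lower-case words, whereas 9.11 defines a capitalised On-therapy day. A reader might infer that 9.12 expressly adopts the compliance rule; it does not. The reading rests on the shared term and on the absence of any other definition. The supplemental SAP, which is not among the documents, may settle it. That stands as a limit on certainty. Still, Section 9.1 presents Sections 9.2 to 9.12 as the full plan, and if a different meaning was intended, the same one-sentence fix removes the doubt.

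**The table is descriptive.** This stands. No efficacy test uses the count. Adverse-event percentages rest on numbers of participants (Sections 9.5.2 and 9.6.2), including the taste-related intervals.

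**Overdose days are not lost to safety review.** A reader might infer that scoring an overdosed day as zero hides a safety signal. It does not. Section 8.5 defines overdose by tablets per day from either bottle, and Table 3 in Section 8.4.1 requires overdoses on treatment to be reported within 5 calendar days.

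**Full-year exposure.** A reader might also infer that almost nobody would be shown with a full year. Section 9.12 plans no count of participants reaching a year, so the plan has no such output to distort.

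**First-to-last-dose duration has its own bias.** It counts interruptions as exposed, whereas the present count errs towards claiming less exposure. This is fair. However, percent compliance is summarized for the same population and will show interruptions. The reverse does not work: two separate sets of summary statistics do not give back each participant's duration.

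**Conclusion.** The point holds as a defect in one descriptive derivation. Read with the only definition the plan gives, 9.12 reports the compliance numerator as duration of intervention and understates time on drug. For a completer with 364 dosing days, the shortfall is about 4, 18, 36 or 73 days at day-level compliance of 99%, 95%, 90% or 80%. It is negligible if dosing is near perfect and reaches a fifth of the treatment period at 80%.

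This rests on two assumptions: that 9.12 takes its term from 9.11, and the compliance levels chosen for illustration. The documents do not support extending the point to the efficacy results, the adverse-event percentages or the detection of overdoses.

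**What to change.** In Section 9.12, define duration of exposure in days as last dose date minus first dose date plus 1. State that the On-therapy-day rule of 9.11 applies to percent compliance only.

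The cost is one sentence. The first dose is given at the site at Visit 3 (Section 8.1.9) and 9.11 already uses the last dose day, so no new data and no change in trial conduct are needed. The small downside is that gaps between first and last dose count as exposed.

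I do not ask for a count of days with any active intake. That would need daily records by bottle, and the documents describe only participant report with tablet counts where possible (Section 6.4) and the time of the last dose before pharmacokinetic sampling (Section 8.6).
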